## Sample Size:

For this study, a total of 234 randomly selected patients with acute undifferentiated febrile illness will be enrolled with a fever of 3 days duration. Of these 234 patients, 117 will be randomly assigned to undergo additional microbiological testing.

Based on previous studies and number of patients needed to include less common seasonal infections, this study will enroll patients throughout a period of 12 months. Cluster sample technique will be used to select 20 patients per month including 10 patients who will be randomly selected to undergo additional microbiological testing.

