## Preliminary work done at Patan Hospital

Patan Hospital is a tertiary care medical center with 450 beds that admits between 10 to 30 febrile patients per week depending on the season. Over 30% of these patients do not have localizing signs and symptoms for clinical diagnosis nor do they have a laboratory-based diagnosis. These cases are labelled as undifferentiated fever and receive empirical treatment with two or more antimicrobial agents. Previous studies done at Patan Hospital have demonstrated that *Salmonella typhi* and *Salmonella paratyphi A* were causes of undifferentiated fever of >3 days duration in 34% patients and *Rickettsia typhi* in 17% cases, whereas another study in 2008 found 7% cases of febrile illness has *Rickettsia typhi*, which is the cause of Murine typhus [5,6]. These studies show an increase in cases of rickettsial infections including *Riackettsia typhi* and *Orientia tsutsugamushi*. Studies at Patan Hospital have also identified *Streptococcus pneumoniae*, *Leptospira* spp., *Orientia tsutsugamushi*, Hantavirus, and *Coxiella burnetii* as casues of febrile illnesses [4-6].

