## j. Data Collection, Data Analysis and Sample Size

Demographic, clinical, radiological, and laboratory data will be collected and entered into a password protected database. To minimize the errors, data will be directly entered into the database using REDCap Database questionnaires.

Data analysis will include the followings:

- 1. Demographics and baseline characteristics of patients will be analyzed and compared between the two groups.
- 2. Clinical diagnosis and laboratory confirmation of diagnosis will be used to estimate the proportions of various infectious etiologies of febrile illness in patients presenting with a febrile illness of 3-21 days duration. (Specific aim-1)
- 3. Number, type, dose and duration of antimicrobials used to treat the patients will be collected and compared between the two groups: clinical diagnosis alone versus clinical plus microbiological diagnosis. (Specific aim 2)
- 4. Appropriateness of the empiric antibiotic therapy will be determined by an independent physician expert after the laboratory confirmation of the diagnosis. Comparison between the two groups (clinical diagnosis vs. microbiological diagnosis) will be done by calculating the proportion of cases who received appropriate antibiotics divided by the total number of cases for whom empiric antibiotics were administered. (Specific aim-3)

- 5. Pretest probability for clinical diagnosis and posttest probability after laboratory-based diagnosis will be calculated and correlated for bacterial, rickettsial, viral infections versus other causes of fever. (Specific aim-4)
- 6. Clinical outcomes will be compared for patients whose treatment is based on clinical diagnosis alone (Group 1) versus the patients whose treatment is based on clinical plus microbiological diagnosis (Group 2). Composite Positive outcome (complete or partial recovery) and Negative outcome (in-hospital death) will be compared between the two groups. (Specific aim-5)

Demographics and baseline characteristics of patients will be expressed in percentages, means±SD, 95% confidence intervals, and/or median±IQR, as appropriate. Proportions will be compared between the two groups with Chi-square tests. Numerical variables will be expressed as Means/SD/95% confidence intervals and Median/IQRs, whereas Student T test or Mann-Whitney test, respectively, will be used for statistical comparisons. Alpha will be set at 95% (level of significance, p <0.05).

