For Specific aims 2 and 3, total daily defined dose (DDD) for each antimicrobial agent received by patients will be calculated following WHO guidelines. The total DDD, number of antibiotics, and Duration of antibiotics used will be compared between the groups by calculating Means/SD/95% confidence intervals. Similarly, appropriateness of antibiotic uses will be tested with cross-tabulation using Chi-square analysis.

For specific aim 4, pre-test probability and post-test probability will be determined by both using standard calculations and using Fagan's Nomogram. Correlations between pre- and post-test probabilities for bacterial, rickettsial, viral vs. other causes will be evaluated.

For specific aim 5, the hazard ratio using the Cox proportional hazard model will be calculated to compare the outcomes between the groups. Since multiple factors, such as comorbidities, severity of illness at baseline, type of infection and host immune status, can influence the outcomes, adjustment for these factors will be considered during the univariate and multivariate outcome analyses. Updated Charlson comorbidity index (Quant et al.) will be calculated and used for comparison between the groups [15]. Similarly, qSOFA will be used to stratify the patients by severity of infection [16].

REDCap (Research Electronic Data Capture) software will be used for questionnaire and database entry. SPSS version 25 (IBM, USA) will be used for statistical analysis.

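### Allocation is described as balanced within month, but the tests named for aims 2 and 3 leave month out: they stay valid, are mildly conservative if use is seasonal, and give up a little precision

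*Protocol*

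**What the plan says.** **Allocation.** The Sample Size section says "this study will enroll patients throughout a period of 12 months", and that the scheme will "select 20 patients per month including 10 patients who will be randomly selected to undergo additional microbiological testing". It calls this a cluster sample technique. It also states the overall split: "Of these 234 patients, 117 will be randomly assigned to undergo additional microbiological testing". One reason given for the year-long enrolment is the "number of patients needed to include less common seasonal infections".

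**Analysis.** Section 5.j says "Proportions will be compared between the two groups with Chi-square tests", and for numerical variables that "Student T test or Mann-Whitney test, respectively, will be used for statistical comparisons". For antimicrobial use it adds: "The total DDD, number of antibiotics, and Duration of antibiotics used will be compared between the groups by calculating Means/SD/95% confidence intervals". Appropriateness of antibiotics (aim 3) is a cross-tabulation with chi-square. Month enters none of these. The only covariate adjustment is in the aim 5 outcome analysis, where the list of factors is open-ended and month is not named.

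**Season.** The section on preliminary work says the hospital "admits between 10 to 30 febrile patients per week depending on the season". No figure is given for seasonal variation in prescribing.

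**The concern.** If 10 of every 20 patients in a month go to each arm, month is balanced by design. Differences between months then cancel out of the arm difference and do not add to its true sampling error. An unstratified test still counts those differences in its standard error. The standard error is too large, p-values are too large and intervals too wide, to the extent that the outcome varies by month.

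The protocol chose a full year partly to capture seasonal infections, so some seasonal variation in treatment is plausible. At stake is precision on primary aim 2, in a single-centre study whose size is limited by budget.

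The label matters too. Patients are randomised individually and every month is sampled, so months are strata. An analyst who took the label literally and applied a cluster design effect to the arm comparison would widen intervals that are, if anything, already too wide.

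**Working it through.** **1. The plan's own figure.** The section on sample size assumptions gives 97 per arm for 90% versus 75% antimicrobial use at 80% power (it attaches this to aim 1; Specific Aims lists antimicrobial use as aim 2). The unpooled two-proportion formula with two-sided 5% gives (1.96 + 0.8416)² × (0.90×0.10 + 0.75×0.25) / 0.15² = 7.849 × 0.2775 / 0.0225 = 96.8, so 97. Then 97 × 1.2 = 116.4, so 117. The stated figures reproduce, and the calculation contains no month term.

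**2. Continuous outcome, closed form.** Let *r* be the share of outcome variance that lies between months. The documents do not give it; 5%, 10% and 20% are assumed. With balance inside each month, the true standard error is √(1−*r*) times the one the test uses. Hence:

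- type I error = 2 × [1 − Φ(1.96/√(1−*r*))]
- power of the planned test, at an effect sized for 80% = Φ(0.8416/√(1−*r*))
- power with month in the model = Φ(2.8016/√(1−*r*) − 1.96)
- excess interval width = 1/√(1−*r*) − 1

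| *r* | Type I error | Excess width | Power, planned | Power, month-adjusted |
|---|---|---|---|---|
| 5% | 4.4% | 2.6% | 81% | 82% |
| 10% | 3.9% | 5.4% | 81% | 84% |
| 20% | 2.8% | 11.8% | 83% | 88% |

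**3. Continuous outcome, simulation.** Twelve months, 10 versus 10 per month, 20,000 runs, standardised difference 0.37 for power.

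| *r* | Type I, t test | Interval coverage | Power, t test | Power, month-adjusted |
|---|---|---|---|---|
| 0 | 0.048 | 0.952 | 0.816 | 0.816 |
| 5% | 0.044 | 0.956 | 0.821 | 0.834 |
| 10% | 0.038 | 0.962 | 0.825 | 0.853 |
| 20% | 0.029 | 0.971 | 0.846 | 0.894 |

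With month in the model, type I error was 0.048 to 0.051 across these rows.

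**4. Binary outcome, simulation.** Same layout, 100,000 runs, monthly rate following a sine curve with an assumed amplitude.

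- Mean 75%, no true difference: chi-square type I error 0.049, 0.050, 0.047, 0.043 and 0.038 at amplitudes of 0, 5, 10, 15 and 20 points.
- Mean 90%, no true difference: 0.053, 0.050 and 0.045 at 0, 5 and 10 points. The 0.053 occurs with no seasonality, so month is not its cause.
- 90% versus 75%: power of chi-square and of the month-stratified Mantel-Haenszel test is 0.879 and 0.876 with no seasonality, 0.882 and 0.882 at amplitudes of 5 and 7.5 points, and 0.886 and 0.895 at 10 and 15 points.

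Around a mean of 90% a sine curve cannot swing by more than 10 points. That caps the month share at (0.10²/2)/(0.90×0.10) = 0.005/0.09 = 5.6%. The 10% and 20% rows above therefore apply to continuous outcomes, not to the control arm of this binary one.

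**5. Does the monthly block close?** 20 × 12 = 240, against 234 stated. Laboratory Methods says only that half of the patients are assigned at random, and the randomisation form in Appendix 1 shows no month block. At 10 febrile admissions a week, with the roughly 30% the protocol reports as undifferentiated, a slow month gives about 3 × 52/12 = 13 candidates, fewer than 20.

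**The case against.** The strongest reply is that nothing here is invalid. Seasonality only pulls the type I error down and coverage up, and the planned test keeps at least its planned 80% power. The loss exists only relative to a more efficient analysis. That stands.

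The month shares are assumed. The documents speak of seasonal infections and seasonal admission numbers, not seasonal prescribing. For the one antimicrobial-use outcome with a sample size, the gain is under one power point. That also stands.

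The monthly figure may be a recruitment target rather than a randomisation block. Under simple randomisation the planned tests would be correctly sized. The mismatch of 240 and 234 and the low-season numbers make this a fair doubt, so the scheme needs confirming.

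Month terms also carry a cost. If both arms were at 90%, about 0.9²⁰ = 12% of months would have no non-user and would contribute nothing. In-hospital death, the negative outcome in aim 5, could leave many strata empty.

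It could be said that month terms belong in a statistical analysis plan. This stands only in part: the protocol itself names the unstratified tests and the cluster label.

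A reader might go further and infer that every between-arm test ignores month. The aim 5 adjustment list is open-ended, so it omits month without excluding it.

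**Conclusion.** The point holds as a modest matter of efficiency and wording. As described, allocation is balanced within month, and the tests named for aims 2 and 3 do not use that balance. If antimicrobial use is seasonal, those tests are mildly conservative. For a continuous outcome with an assumed month share of 5% to 20%, type I error is about 4.4% to 2.8%; at 10% to 20%, month adjustment adds about 3 to 5 power points. For 90% versus 75% it adds under 1 point, and with no seasonality it adds nothing.

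Two stronger readings are not supported. A reader might infer that the 5% level and 95% intervals fail, but the departure is only in the safe direction. A reader might also infer that the trial falls short of its planned power, but it does not. All of this assumes that the 10-of-20 split is a real monthly block and that prescribing varies by month. The documents settle neither.

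**What to change.** In section 5.j:

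- Replace the cluster-sample wording with allocation stratified (blocked) by enrolment month, and reconcile 20 × 12 = 240 with 234. If 20 per month is only a recruitment target, say so; the named tests then match the randomisation and month is an optional covariate.
- If the monthly block is real, include month as a stratum in the aim 2 and 3 comparisons: a linear model with month terms, or the van Elteren test, for total DDD, number and duration of antimicrobials; Mantel-Haenszel for proportions.
- Use calendar quarter where month strata are sparse, notably for in-hospital death in aim 5.

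The cost is small. Month can be taken from the admission date already on the randomisation form; a patient admitted late in one month and randomised in the next would need the randomisation date, which that form does not list. At most 11 degrees of freedom are used, so with 234 patients the residual falls from 232 to 221. A few strata will be uninformative for binary outcomes. No extra patients or tests are needed.

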#### Sample size determination and assumptions:

For specific aim 1, a reduction of antimicrobial use in about 15% patients is expected after additional laboratory confirmation of the diagnosis including viral infections. Assuming this decrease in antibiotics from 90% to 75%, 95% confidence interval, and 80% power, required sample size would be 97 in each arm. With similar assumptions for specific aim 3, an improvement in antimicrobial therapy from 70% to 90% would require 59 patients.

For specific aim 2, assuming an improvement in identification of causative agents from 30% to 50%, 95% confidence interval, and 80% power, required sample size would be 91.

For specific aim 5, an improvement in clinical outcome for patients whose treatment is based on microbiological diagnosis by 20%, from 60% to 80%, 95% confidence interval, and 80% power, the required sample size would be 79 in each arm.

Based on above calculations, minimum sample size needed would be 97 in each arm. Including a 20% loss for failure to consent and loss to follow up, total sample size needed will be 117 in each arm.

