#### e. Informed Consent

Patients admitted to the Medical Ward with febrile illness will be screened for the study inclusion and exclusion criteria. Patients who meet all inclusion criteria and none of the exclusion criteria will be enrolled in the study after taking written voluntary consent on an Informed Consent Form (ICF) approved by the institutional research committee (IRC). If patient is unable to give consent, his or her legal guardian will be contacted for written consent on behalf of the patient.

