#### i. Follow up and Expected Outcomes

During the hospital stay, patients will be followed up for new laboratory results, changes in treatment plan and outcomes. The patient outcomes will be recorded as:

- a. time to defervescence;
- b. de-escalation or readjustment in antimicrobials;
- c. complete recovery and discharge vs. partial recovery and discharge vs. death.

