## 6. PROTECTION OF HUMAN SUBJECTS (ETHICAL CONSIDERATIONS)

This clinical research project will be submitted for a full board approval by the PHAS Institutional Research Committee. Patients will be enrolled from Patan Hospital's inpatient ward after taking informed consent on an informed consent form (ICF) as approved by the PAHS IRC. All patients will be provided written information about the study in Nepali language before enrollment. For patients who

DEFINe Project Principal Investigator: [name]

are unable to understand Nepali, either a family member or a hospital staff will be used as an interpreter to overcome the language barrier and to help the patient understand the study process and its potential harms and benefits.

This project will have equal opportunities for inclusion of women and minorities. Children will be excluded because of a different spectrum of infectious agents outside the scope of this study.

All personal data collected for the study will be stored in a confidential manner in a secure computer with password protection. Only the research team and assigned data analyst will have access to the database. Any new information received during the study will be revealed to the patient. Patients enrolled in the study will be able to withdraw their consent at anytime they wish. Any serious adverse events will be reported to the IRC.

**Registration:** After IRC approval, this study will be registered at Clinical Trial.gov.

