#### Patient should meet none of the Exclusion criteria below:

No.	Question	Yes	No
b7	Children (younger than 16 years in age)**		
b8	Fever of less than 3 days or more than 21 days duration		
b9	Outpatients		
b10	Patients being discharged from Emergency Room		
b11	Immunocompromised patients		
b12	Neutropenia (ANC <500 per cumm)		
b13	Known case of HIV infection		
b14	Hospital admission for 48-hours or longer within past 30 days		
b15	Patient does not meet any of the above exclusion criteria		

(\*\*Children under 16 years will be excluded since they have different causes of febrile illnesses requiring a different set of lab tests which is beyond the scope of this study.)

If patient meets all of Inclusion criteria and none of the exclusions, proceed with patient consent followed by randomization and enrollment.

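### The 20% loss allowance is applied as 97 × 1.2 = 117 per arm, which keeps the required 97 only up to 17.1% loss, and it counts refusals that occur before randomisation

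*Protocol*

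**What the plan says.** Protocol section 5.j (Sample size determination and assumptions) bases the size on a fall in antimicrobial use from 90% to 75% with 80% power, and concludes that the "minimum sample size needed would be 97 in each arm". It then inflates: "Including a 20% loss for failure to consent and loss to follow up, total sample size needed will be 117 in each arm".

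The preceding Sample Size paragraph treats the inflated figure as patients already in the trial. It speaks of 234 enrolled, and adds: "Of these 234 patients, 117 will be randomly assigned to undergo additional microbiological testing".

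Elsewhere the protocol fixes when each kind of loss can occur:

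- **Refusal.** Signed consent is an inclusion criterion (5.c). Section 5.e says eligible patients "will be enrolled in the study after taking written voluntary consent", and Appendix 1 (B) tells staff to "proceed with patient consent followed by randomization and enrollment".
- **Loss after randomisation.** Follow-up is in hospital (5.i: "During the hospital stay, patients will be followed up for new laboratory results"). Section 6 adds: "Patients enrolled in the study will be able to withdraw their consent at anytime they wish".

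The budget (section 11) prices serology as 7x97 tests and other laboratory supplies for 97.

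**The concern.** There are two faults in one sentence.

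- **Wrong operation.** To have 97 left after a proportion d is lost, one enrols 97/(1 − d). Multiplying by (1 + d) enrols too few, because the loss acts on the larger, enrolled number.
- **Mixed losses.** A refusal before randomisation raises the number to be screened but takes nobody out of an arm. Only loss after randomisation reduces the number analysed. With both in a single 20%, the loss that matters for power is unknown.

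The reader therefore cannot tell from this section whether 117 per arm delivers the 97 on which the 80% power rests.

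**Working it through.** **Inputs.** Rates 90% and 75%, 80% power, minimum 97 per arm, 20% allowance and 117 per arm, all from 5.j (Sample size determination and assumptions). Significance level 0.05, from 5.j. Two-sided testing is an assumption, since the protocol does not say, but it reproduces the protocol's figure.

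**1. Reproduce the 97.** Two proportions, normal approximation, unpooled variance:

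n = (1.960 + 0.842)² × (0.90 × 0.10 + 0.75 × 0.25) / 0.15² = 96.8, rounded up to 97.

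The same formula gives 58.9, 90.3 and 78.5 for the protocol's other three comparisons, which round up to its 59, 91 and 79. It is therefore the formula used, and the base figure is sound on its own assumptions. (The pooled formula would give 99.5, so 100.)

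**2. Reproduce the 117.**

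- 97 × 1.2 = 116.4, rounded up to 117. This matches.
- 97 / 0.8 = 121.25, rounded up to 122. This does not match.

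**3. What 117 preserves.**

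- After 20% loss: 117 × 0.8 = 93.6, so 93 to 94 remain, 3 to 4 short of 97.
- Largest tolerable loss: (117 − 97)/117 = 20/117 = 17.1%.

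**4. Power by loss after randomisation.** Power = Φ(0.15 / √(0.2775/n) − 1.960), where 0.2775 = 0.09 + 0.1875. The documents give no figure for this loss alone, so the range is an assumption.

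| Loss after randomisation | Left of 117 | Power, 90% v 75% | Enrolment per arm needed to keep 97 |
|---|---|---|---|
| 0% | 117 | 86.9% | 97 |
| 5% | 111 | 85.1% | 103 |
| 10% | 105 | 83.1% | 108 |
| 15% | 99 | 80.9% | 115 |
| 17% | 97 | 80.1% | 117 |
| 20% | 93 to 94 | 78.4 to 78.8% | 122 |

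Other methods agree on the size of the change. At 93 / 94 / 97 per arm, the pooled formula gives 77.2 / 77.7 / 79.0% and the exact Pearson chi-square calculation 78.3 / 78.8 / 80.2%.

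**5. Does either reading of 117 work?**

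- If 117 are patients approached, a combined 20% loss leaves 93 to 94, below 97. This reading also conflicts with the Sample Size paragraph, which counts them as enrolled and assigned.
- If 117 are patients randomised, refusals have already happened and do not belong in the allowance.

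**6. Budget.** Serology: 500 × 7 × 97 = 339,500. Supplies: 200 × 97 = 19,400. Adding 12,900 + 16,414 + 7,686 + 10,000 gives Rs. 405,900, the stated total, so 97 is the quantity used. Cost per tested patient is 7 × 500 + 200 = 3,700. Testing 117 would cost 432,900 against 358,900 for 97, a gap of Rs. 74,000. This is an upper bound, because the section on additional evaluations runs the panel only when routine tests are inconclusive. Since eligibility already requires no obvious diagnosis on those tests, the true gap may lie close to the bound.

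**The case against.** The strongest reply is that the shortfall may never occur. It needs more than 17.1% lost after randomisation, and taking refusals out of the 20% brings that loss below 20%. Patients are inpatients, follow-up is confined to the stay, and antimicrobial use is recorded as treatment received, so there is no later visit to miss. At 5 to 15% loss, power is 80.9 to 85.1%. This stands, and it is why the point is one of justification and not a call for more patients. It does not rescue the derivation, because the protocol neither separates the two losses nor states the one that matters.

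The Sample Size paragraph also plans 20 patients per month for 12 months, which is 240, or 120 per arm. That would keep 97 up to 23/120 = 19.2% loss, but a full 20% would leave 96 (79.7% power), and the stated target is 234.

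The worst case is no larger than the effect of choosing a formula: pooled power at 97 is already 79.0%. That is a fair statement of size.

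The 97 also rests on a binary outcome, while the analysis text for antimicrobial use lists total DDD, number of agents and duration. That is true, but it is a separate matter: the power figures here describe only the comparison the protocol used to set its size.

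Finally, the budget mismatch is financial and adds no weight to the sample size point.

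**Conclusion.** The concern holds. The stated 117 does not follow from a minimum of 97 and a 20% loss, and the 20% includes refusals that cannot deplete a randomised arm. The consequence is small: at most 3 to 4 patients per arm and under 2 points of power, arising only if loss after randomisation exceeds 17.1%. That loss is not given in the document, so whether 117 is enough cannot be settled from it; it may well be. The power figures assume two-sided testing at 0.05 and the 90% v 75% comparison. The point merits correction because this calculation sets the size of the whole trial and is wrong as written. The mismatch between 97 tests budgeted and 117 patients assigned to testing is real but secondary.

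**What to change.** In section 5.j (Sample size determination and assumptions):

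1. Take failure to consent out of the loss allowance and use it to set the number screened.
2. State the expected loss after randomisation on its own (withdrawal and in-hospital loss), and say that 117 per arm keeps 97 evaluable up to 17% loss.
3. Alternatively, keep the 20% as post-randomisation loss and restate power as 78 to 79%. The matching enrolment of 122 per arm (244 in total, 10 more than planned) is needed only if a full 20% loss after randomisation is assumed and 97 is to be kept.

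In section 11, reconcile the 97 tested patients with the 117 assigned to testing, or say why they differ.

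Cost: one or two restated sentences, no added patients under options 1 and 2 or the restated power, and one budget quantity corrected or explained (at most Rs. 74,000).
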